1. To determine the feasibility of Mindfulness Based Stress Reduction (MBSR) for older cohabiting, intimate couples in which one, or both partners, has metabolic syndrome. We will (a) monitor recruitment, (b) adherence, and (c) missing data for the intervention. We will explore how being a couple impacts the MBSR experience, assessing (a) the prevalence of both partners having metabolic syndrome versus one partner, (b) shared decision making about participation and adherence, (c) how MBSR can be tailored to the needs of older couples, and (d) the impact on relationship quality and shared health behaviors.

2. To determine whether MBSR improves self-reported physical health status (SF-36) (Ware Jr & Sherbourne, 1992) for each partner. Hypothesis 1: The intervention group will have a significantly greater score on the SF-12 scale than does the control group.

3. To determine if MBSR reduces perceived stress (Perceived Stress Scale (Roberti, Harrington, & Storch, 2006)) and increases mindfulness (Kentucky Inventory of Mindfulness Skills (Baer, Smith, & Allen, 2004)). Hypothesis 2: Perceived stress will be reduced and mindfulness will increase for the MBSR group compared to the control group.

4. Exploratory aim: To determine if an MBSR intervention is associated with decreases in the composite measure of metabolic syndrome (blood pressure, waist circumference, glucose levels, cholesterol, triglycerides) for each partner. Hypothesis 3: The metabolic syndrome composite score for partners will be smaller at the end of the study in the MBSR group compared to the control group.

2. Background:

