Metabolic syndrome is a common multifactorial disorder that increases risk for cardiovascular disease and diabetes and affects a substantial proportion of older adults(Eckel, Grundy, & Zimmet). Between 23 and 55% of older adults meet metabolic syndrome criteria, which consists of having three of the following: abdominal obesity, hypertriglyceridemia, low high-density lipoprotein (HDL) cholesterol, high blood pressure, and high fasting glucose (Denys et al., 2009). Although this is a common syndrome, there are few preventive interventions targeting metabolic syndrome (Dunkley et al., 2012). This is despite the fact that the NHLBI suggests that treatment start with lifestyle changes including diet, exercise, maintaining healthy weight, and stress reduction, with medications as a secondary treatment. With the increasing number of medications that older adults take (Charlesworth, Smit, Lee, Alramadhan, & Odden, 2015), lifestyle interventions are becoming even more important. To date, most lifestyle interventions target diet and exercise without explicitly addressing stress reduction. As stress is related to overall psychological and physical health as well as each metabolic syndrome biomarker (Matthews & Kuller, 2002), research on the efficacy of stress reduction interventions for older adults is critical.

Lifestyle interventions that target older couples may be more effective than lifestyle interventions that target older individuals. The majority of older adults (especially men) are in close, committed relationships (US Census Bureau). Within close relationships, especially older intimate cohabiting couples, partners' characteristics and environments make them similar not only in terms of stress, but also health behaviors and mental and physical health (Hoppmann, Michalowski, & Gerstorf, 2016). Partners also have important positive and negative influences on each other. By targeting both partners within a couple, lifestyle interventions have the capability of maximizing the positive influences and minimizing the negative influences. There is some preliminary evidence that this is the case, as multiple weight control interventions show added benefit of involving relationship partners in their programs (Black, Gleser, & Kooyers, 1990).

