Importantly, we will explore the dyadic effects of couple members' simultaneous engagement in the MBSR intervention. In addition to using proper statistical techniques to understand the effects of MBSR on each partner's outcomes, we will examine partner influences. For each primary hypothesis, we will examine the secondary hypothesis that each partner's improvement in each health outcome (self-report physical health, stress, mindfulness, and metabolic syndrome composite biomarker score) will be associated with improvement in the other partner's health outcome. In addition, we will examine the effects of the intervention on both partners' relationship satisfaction. Showing that relationship satisfaction can be enhanced is an important goal on its own, but we may also find that health outcomes improve when relationship quality improves.

3. Research Plan:

Procedures

Forty couples (N=80) will participate in a baseline visit to have blood drawn, BMI and BP measured, and to complete questionnaires assessing demographics, contextual factors, and baseline primary outcomes. Couples will be randomized to the MBSR condition (n=20 couples/ 40 individuals) or the wait list control condition (n=20 couples). The baseline blood draws and survey administration will take place at the CSRU, with the HRU as back up as needed. The blood analysis will be done by the YCCI Core lab. All participants will receive an informational sheet about metabolic syndrome.

Participants will be randomized to the intervention or wait-list group after informed consent is obtained, the initial blood is drawn and survey baseline is completed at the CSRU. A random digit generator will be used that assigns a condition (in this case, intervention or wait list) to each couple ID number.

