Physical health symptoms (SF-12)	12	Primary outcome		X	X
Perceived stress scale (Roberti et al., 2006)	10	Primary outcome		X	X
Kentucky Inventory of Mindfulness Skills (Baer et al., 2004)	39	Primary outcome		X	X
Relationship Assessment Scale (Hendrick, 1988)	7	Secondary outcome		X	X
Health behavior questionnaire (sleep, physical activity, eating behavior, medication adherence (Schulz et al., 1997))	22	Secondary outcome		X	X
Couples' decision making in participation and adherence: 1) How was your partner involved in your decision to first participate in the intervention? (Responses: a. encouraged you, b. discouraged you, c. neither) 2) How was your partner involved in your decision to continue with each class? (Responses: a. encouraged you, b. discouraged you, c. neither) 3) Open ended question: Describe how participating with your partner influenced your experience with the intervention.	3	Exploring couple dynamics			X
Biological Measures (Both partners)					
Blood draw: to assess hypertriglyceridemia and low high-density lipoprotein (HDL) cholesterol and high fasting glucose	3	Secondary outcome		X	X
Abdominal obesity- waist circumference per WHO protocol (2011)	1	Secondary outcome		X	X
Blood pressure (automated Carescape cuff)	1	Secondary outcome		X	X
Do both partners, only the husband, or only the wife have metabolic syndrome at baseline?	1	Exploring couple dynamics			
Feasibility Measures (Both partners)					
Percent of couples who screen versus enroll (Project manager keeps a record.)	1	Feasibility outcome	X		
# of MBSR sessions attended (Interventionist takes attendance.)	1	Feasibility outcome			X
Total minutes of home MBSR practice (Participants keep a daily record.)	1	Feasibility outcome			X

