Feasibility outcomes will be observed, recorded, and qualitatively evaluated. Descriptive characteristics of the cohort will be summarized with means and standard deviations and counts and percentages according to intervention group. Although this pilot study will not be powered to test all outcomes for statistical significance, the primary quantitative outcomes are expected to have continuous Gaussian distributions making possible the comparison of intervention and control group results with linear mixed effects regression models that can accommodate the clustering of outcome results within couples. Finally, in anticipation of future studies of the metabolic syndrome outcome,

selected analyses will be conducted to compare the utility of the composite metabolic syndrome outcome and with a version of this outcome yielded by a measurement model in a structural equation modeling context.

Hypothesis 1: Self-reported physical health will be greater on average for participants in the MBSR intervention group compared to a wait-list control group. A multivariable linear mixed effects model will be used to assess whether self-reported physical health is greater in the intervention group than in the control group. A random effect will be used to account for the clustering of outcome values within couples. A pre-specified set of covariates will be entered into the regression model including baseline self-reported physical health and demographics and contextual factors that differ significantly across intervention and control groups. Model goodness of fit will be assessed with residual analysis, influence statistics, and goodness-of-fit statistics.

Hypothesis 2: MBSR will reduce each partner's self-reported stress and increase their mindfulness. The analyses for these two secondary outcomes will proceed according to the same procedures as cited for Hypothesis 1 above.

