Hypothesis 3: The metabolic syndrome composite score for participants will be smaller at the end of the study in the MBSR group compared to the control group. Given the exploratory nature of this hypothesis and the lack of consensus as to how to code a variable for metabolic syndrome, this Hypothesis 3 will be analyzed in three different ways: 1) with the outcome as a binary indicator variable indicating the occurrence of 3 or more of the 5 syndrome components; 2) with the outcome as a continuous variable obtained from the summation of Z-score transformations of the 5 syndrome components; and 3) as continuous latent factor or principal component construct obtained from a factor analytic measurement model. Performing these three analyses will provide invaluable insights for determining how the metabolic syndrome outcome will be coded in future studies using older samples.

We will explore the dyadic effects of couple members' simultaneous engagement in the MBSR intervention. In addition to the above analyses, we will use SPSS mixed models for analyzing repeated measures in couples. In this analytic approach, reports of health (primary outcome) (Level 1) are nested within time-invariant individual and couple variables (i.e., background variables, intervention condition (primary predictor), and moderators) at Level 2. The program allows for the analysis of intercepts and slopes of the hypothesized associations between Level 1 variables (i.e., within-couple relations between each partner's health) across all assessment points (baseline, 8 weeks, and 3 months), as well as interactions between Level 2 variables and Level 1 intercepts and slopes. In other words, we will assess whether the intervention was successful at the couple level by looking at the overall intervention effect, as well examine, for heterosexual couples, differential effects for husbands and wives by looking at the role (husband or wife) X intervention interaction.

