A Certificate of Confidentiality is not needed and therefore has not been obtained.

- h. Are any of the study procedures likely to yield information subject to mandatory reporting requirements? (e.g. HIV testing – reporting of communicable diseases; parent interview -incidents of child abuse, elderly abuse, etc.). Please verify to whom such instances will need to be reported.

No.

SECTION V: POTENTIAL BENEFITS

Potential Benefits: Identify any benefits that may be reasonably expected to result from the research, either to the subject(s) or to society at large. (Payment of subjects is not considered a benefit in this context of the risk benefit assessment.)

The potential improved patient satisfaction, functional status, and quality of life for older adults with metabolic syndrome can have far reaching implications, including greater receptivity to the benefits of interventions, superior adherence, and enhanced resiliency to the inevitable variations in chronic disease presentation. Adding MBSR to metabolic syndrome treatment regimens could provide tremendous benefit to the many older adults, in addition to relieving a sub-optimal and overburdened healthcare system. The relative risk to subjects participating in this pilot study is negligible. The greatest risk may be

that subjects are involved in alternative treatment that ultimately proves to be no more effective than the usual care they have already received. Thus, the risk-benefit ratio strongly favors the study participant.

The identification of a practical stress reduction regimen of that can produce symptomatic and psychological relief has the potential to help alleviate the suffering of patients with metabolic syndrome and improve public health. Results obtained from this initial line of inquiry will be the first step in developing a graduated, stepwise integrative medicine algorithm for the treatment of metabolic syndrome in older adults. The long-term intention is to expand this approach to a larger sample and to older couples with other types of medical risk factors.

SECTION VI: RESEARCH ALTERNATIVES AND ECONOMIC CONSIDERATIONS

1. **Alternatives:** What other alternatives are available to the study subjects outside of the research?

Alternatives to participating in the study would be to continue with their usual medical care, often involving pharmacotherapy.

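### Hypothesis 3, binary coding: one end-of-study outcome counts resolution in affected people and only new onset in unaffected partners, so the arm difference depends on how many unaffected partners enrol

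*Protocol*

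**What the plan says.** Protocol, Section I, item 1 (Aim 1) defines the population as "older cohabiting, intimate couples in which one, or both partners, has metabolic syndrome". Under item 3, Procedures, "Forty couples (N=80) will participate in a baseline visit", and couples are then randomised 20 to each arm.

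Item 13 (Statistical Considerations) predicts a smaller metabolic syndrome composite in the MBSR arm than in the control arm at the end of the study. It calls this hypothesis exploratory and codes the outcome three ways. Coding 1 is the binary one: "with the outcome as a binary indicator variable indicating the occurrence of 3 or more of the 5 syndrome components". Codings 2 and 3 are continuous (a sum of Z-scores, and a latent factor or principal component). No coding is limited to people who have the syndrome at baseline, and no baseline adjustment is stated for this hypothesis. The covariate-adjusted model of Hypothesis 1 is carried over explicitly to Hypothesis 2 only.

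The Measurement Schedule does record each partner's status ("Do both partners, only the husband, or only the wife have metabolic syndrome at baseline"), but under the exploration of couple dynamics. The one treatment interaction that item 13 names is with husband or wife role. Its dyadic model also mentions moderators without listing them.

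**The concern.** Coding 1 puts two different events into one indicator. For someone who starts with 3 or more components, the end-of-study value shows whether the syndrome persisted or resolved. For a partner who starts below 3, it shows only whether the syndrome newly appeared. Such a partner cannot contribute a resolution, and can support the hypothesis only if MBSR prevents onset during a follow-up of 8 weeks to 3 months.

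Two things follow. The arm difference depends on the mix of couples that happens to enrol, which is unknown in advance. And an unadjusted comparison carries the large, predictable difference between affected and unaffected people as noise.

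This matters even for an exploratory outcome because the protocol intends to use it. Item 2 expects Aim 4 to supply effect sizes for longer studies, and item 13 says that comparing the three codings will guide how future studies code the outcome. As it stands, coding 1 could look poor because of its denominator and not because of the coding.

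**Working it through.** The protocol gives no power or sample size figure for Hypothesis 3, so there is none to reproduce. Its only power statement concerns the SF-12.

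**Inputs from the protocol.** 80 participants, 40 per arm. At least one partner per couple is affected. Background: "Between 23 and 55% of older adults meet metabolic syndrome criteria".

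**Assumptions.** Exactly one partner per couple is certain to be affected, and the other is affected with probability p, from 0.23 to 0.55. Resolution among the affected is 10% in controls and 40% with MBSR. Onset among the unaffected is 5% in both arms. Couple clustering and dropout are ignored. The event rates are illustrative and not from the protocol.

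**Step 1, affected share.** f = (1 + p)/2.
- p = 0.55: f = 0.775, so 62 of 80 are affected and 18 are not.
- p = 0.23: f = 0.615, so 49.2 of 80 are affected and 30.8 are not.
- The logical limits are 0 to 40 unaffected.

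**Step 2, end-of-study occurrence.** Proportion = f × (1 − resolution) + (1 − f) × onset.
- p = 0.55: control 0.775 × 0.90 + 0.225 × 0.05 = 0.709; MBSR 0.775 × 0.60 + 0.225 × 0.05 = 0.476; difference 0.2325.
- p = 0.23: control 0.615 × 0.90 + 0.385 × 0.05 = 0.573; MBSR 0.615 × 0.60 + 0.385 × 0.05 = 0.388; difference 0.1845.
- With equal onset in the two arms, the difference is simply f × 0.30.

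**Step 3, power, two-sided 5%.** With n per arm, proportions p1 and p2, and mean m: Φ{(|p1 − p2| − 1.96 √[2m(1 − m)/n]) / √[(p1(1 − p1) + p2(1 − p2))/n]}.
- p = 0.55, all participants (n = 40, m = 0.5925): (0.2325 − 0.2153)/0.1068 = 0.16, power 56%. Affected only (n = 31, m = 0.25): (0.30 − 0.2156)/0.1032 = 0.82, power 79%.
- p = 0.23, all participants (n = 40): power 38%. Affected only (n = 24.6): power 69%.

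**Step 4, keeping everyone but stratifying by baseline status.** The stratum differences are weighted by stratum size, with SE = √[f × 0.33/40 + (1 − f) × 0.095/40]. Here 0.33 = 0.10 × 0.90 + 0.40 × 0.60, and 0.095 = 2 × 0.05 × 0.95. Power is Φ(difference/SE − 1.96). For a like-for-like comparison, all three versions below use this unpooled variance.

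| Analysis | p = 0.55 | p = 0.23 |
|---|---|---|
| All participants, unadjusted | 59% | 39% |
| All participants, stratified | 80% | 66% |
| Affected only | 83% | 74% |

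**Step 5, sensitivity (Step 3 formula unless noted).**
- Resolution 10% versus 30%: 19-30% unadjusted against 42-50% in the affected.
- Resolution 10% versus 20%: only 17-20% even in the affected (unpooled variance).
- p = 0.80: 74% against 85%, so the loss has the same direction and is smaller.
- Onset 10% in controls and 5% with MBSR: the stratified analysis reaches 72-82% (unpooled variance).

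**The case against.** The strongest case against is that the hypothesis is a between-arm contrast at the end of the study, so an unaffected partner does count in its favour if MBSR prevents onset. That is correct, and the shrinkage above depends on no such benefit. Even then, one number would mix resolution with prevention.

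It can also be said that the power loss is mostly a matter of missing baseline adjustment. That stands in large part: Step 4 shows that stratifying recovers most of the loss without dropping anyone. Model details often sit in an analysis plan, and one may exist here. But the protocol itself fixes the outcome and the population of coding 1, and those cause the mixing.

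The illustration is favourable too. Item 2 concedes that biomarkers may be hard to shift in so short a time. It also describes partners as similar in health, which would leave fewer unaffected partners. Both points limit the size of the loss but do not reverse its direction.

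A reader might infer two stronger things, and the protocol supports neither.
- **That Hypotheses 1 and 2 are diluted as well.** Physical health, stress and mindfulness can improve in either partner. The aims address both partners, and item 13 targets an average over participants ("Self-reported physical health will be greater on average for participants in the MBSR intervention group"). Dilution would need an effect confined to affected people, which the protocol does not assume. Codings 2 and 3 of Hypothesis 3 likewise let everyone improve.
- **That the effect in people with the syndrome will never be estimated.** No such analysis is named, but the status is collected, unlisted moderators are allowed, and an analysis plan could add it.

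**Conclusion.** The point holds for coding 1 of Hypothesis 3 only. Applied to all participants without regard to baseline status, the binary outcome means different things for the two kinds of partner, and its arm difference varies with the enrolment mix. Under the stated assumptions, the difference falls from 30 points to 18-23, and power from 69-79% to 38-56%. These figures rest on assumed event rates, on general prevalence standing in for the second partner's, and on ignoring clustering. If true effects are smaller, every version is underpowered and the gain is chiefly in interpretation.

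Because the outcome is exploratory in a pilot, no primary conclusion is at risk. What is at risk is the usefulness of the binary effect size and of the comparison between codings. This is an inexpensive improvement worth making.

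**What to change.** For coding 1, compare between arms the share who no longer meet the definition among participants with 3 or more components at the baseline visit, and list new onset in the other partners descriptively by arm. Restricting on a variable measured before randomisation keeps the comparison randomised. If all participants are to stay in, stratify or adjust the binary analysis by the person's own baseline status. Either way, say that status comes from the baseline visit measurements, because eligibility is confirmed from the medical chart and the two may differ.

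Optionally, for codings 2 and 3, report the arm effect with a 95% confidence interval by baseline status as exploratory estimates. Leave Hypotheses 1 and 2 as they are.

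The cost is a few lines of analysis text, since the variable is already collected. The restricted analysis would use about 49 to 62 people instead of 80 under the prevalence range above, and any estimates in unaffected partners will have wide intervals.

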How quantitative and qualitative data will be combined to understand outcomes. Qualitative data will be analyzed using Atlas.ti software and themes will be identified regarding partner influence on study experience. Key demographic characteristics and results from quantitative questions regarding decision making in participation and adherence will be entered into the software as coded attributes. Queries will be conducted to investigate the relationships between identified themes and coded attributes. Finally, the results of this qualitative analysis will be used to formulate hypotheses about the meanings and mechanisms underlying the quantitative results for Hypotheses 1 and 2, and especially, for the results of dyadic analyses of couple members' simultaneous engagement in the MBSR intervention.

Power: The sample size procedure in PASS shows that in anticipation of loss-to-follow-up, and with recognition of dependency in results from couples, the effective sample size is estimated to be 70, a reduction of 10 from the enrollment of 80 study participants. Assuming power of 80%, an outcome standard deviation of 10, and equal assignments to the intervention and control groups, this effective sample size will allow for detection of a difference between intervention and control groups mean values for the SF-12 outcome of 6.43 or more at the two-sided level of significance of 0.05. The sample size procedure in PASS was performed.

SECTION III: RECRUITMENT/CONSENT AND ASSENT PROCEDURES

1. Targeted Enrollment: Give the number of subjects: 80 participants

- a. Targeted for enrollment at Yale for this protocol: 80
- b. If this is a multi-site study, give the total number of subjects targeted across all sites: N/A

2. Indicate recruitment methods below. Attach copies of any recruitment materials that will be used.

- | | | |
|---|---|-------------------------------------|
|  Flyers |  Internet/Web Postings |  Radio |
|  Posters |  Mass E-mail Solicitation |  Telephone |
|  Letter |  Departmental/Center Website |  Television |
|  Medical Record Review* |  Departmental/Center Research Boards |  Newspaper |

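### The single reduction from 80 to 70 covers both loss to follow-up and partner correlation only if both are small, so the effective sample size is probably optimistic

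*Protocol*

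**What the plan says.** The protocol's only power statement is the Power paragraph of Section I, item 13 (Statistical Considerations). According to it, "the effective sample size is estimated to be 70, a reduction of 10 from the enrollment of 80 study participants". This one reduction is made for two reasons, "in anticipation of loss-to-follow-up, and with recognition of dependency in results from couples". Further inputs are "an outcome standard deviation of 10, and equal assignments to the intervention and control groups", 80% power, and a test "at the two-sided level of significance of 0.05". The result is a detectable difference in "mean values for the SF-12 outcome of 6.43 or more". No loss rate and no within-couple correlation is given.

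Three other places bear on the reduction:

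- Section I, item 3 (Procedures) randomises whole couples, 20 per arm.
- Section I, item 2 (Background) says of partners that their "characteristics and environments make them similar not only in terms of stress, but also health behaviors and mental and physical health".
- Item 13, Hypothesis 1, plans a mixed model with a random effect for couple and adjustment for baseline self-reported physical health.

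**The concern.** Loss to follow-up and partner correlation each reduce information, and their effects multiply. A total reduction of 12.5% (10 of 80) leaves little room for both. If most of it is used for loss, the implied correlation between partners is close to zero. That fits poorly with a study whose rationale is that partners resemble and influence each other, and which plans to test whether one partner's improvement is associated with the other's.

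The protocol's one quantitative statement about what the trial can detect rests on the figure of 70. If 70 is too high, the detectable SF-12 difference is larger than a calculation from 70 would show. Correcting only the step from 70 to the detectable difference would leave this untouched.

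**Working it through.** **Inputs from the protocol.** 80 enrolled; couples randomised 1:1, so cluster size 2; SD 10; two-sided 0.05; 80% power; effective N 70; difference 6.43. Loss and ICC are not given and are assumed below.

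**Step 1: the plan's own figure.** For two equal groups with total N, the difference detectable with 80% power is, by the normal approximation, (1.960 + 0.842) × 10 × √(4/N).

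- At N = 70 this is 2.802 × 10 × 0.2390 = 6.70. The t-test (noncentral t, N − 2 degrees of freedom) gives 6.79.
- Power at 6.43 with N = 70 is 76.7% (normal) or 75.5% (t).
- A difference of 6.43 needs 2 × (2.802 × 10 / 6.43)² = 37.97, so 38 per arm or 76 in total (normal), or 78 in total by the t-test (6.426).

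The stated 6.43 therefore does not follow from 70. The baseline for judging the input of 70 is 6.79 and 75.5%, not 6.43 and 80%.

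**Step 2: what 70 implies.** With pairs as clusters the design effect is 1 + ICC, so effective N = 80 × (1 − loss) / (1 + ICC). Setting this to 70 gives ICC = 80 × (1 − loss)/70 − 1.

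| Loss | Retained | Largest ICC compatible with 70 |
|---|---|---|
| 0% | 80 | 80/70 − 1 = 0.143 |
| 5% | 76 | 76/70 − 1 = 0.086 |
| 10% | 72 | 72/70 − 1 = 0.029 |
| 12.5% | 70 | 70/70 − 1 = 0 |

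**Step 3: effect of other inputs (assumed), t-test, SD 10.**

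| Loss | ICC | Effective N | Difference at 80% power | Power at 6.43 |
|---|---|---|---|---|
| 70 as stated | – | 70 | 6.79 | 75.5% |
| 5% | 0.05 | 76/1.05 = 72.4 | 6.68 | 77% |
| 5% | 0.1 | 76/1.1 = 69.1 | 6.84 | 75% |
| 10% | 0.1 | 72/1.1 = 65.5 | 7.03 | 73% |
| 10% | 0.2 | 72/1.2 = 60.0 | 7.36 | 69% |
| 10% | 0.3 | 72/1.3 = 55.4 | 7.67 | 65% |

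With 10% loss and ICC 0.2, the part due to the input of 70 is 7.36 − 6.79 = 0.57 points and 75.5 − 68.8 = 6.7 percentage points of power.

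**Step 4: does joint dropout matter?** The formula assumes that couples leave together. If individuals leave independently at 10%, the expected contribution per couple at ICC 0.2 is 0.81 × 2/1.2 + 0.18 × 1 = 1.53. Over 40 couples that is about 61, against 60 above, so the conclusion does not depend on this.

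**The case against.** A reader might infer that a reduction of 10 cannot cover both reasons. The documents do not support that: 5% loss with ICC 0.05 gives 72.4, which is above 70. The protocol also gives some reason to expect low loss. Item 3 (Recruitment, data management and retention) cites complete datasets in an investigator's other studies, a short intervention and payment at each visit. Those studies are in other conditions, however, and the Power paragraph itself anticipates loss. Even with no loss, 70 allows an ICC of only 0.14.

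The Background statement on partner similarity is qualitative. It gives no size for the correlation and does not refer to SF-12 scores at follow-up. It argues against a value near zero but does not establish 0.2 or 0.3, which are assumptions here.

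A reader might also blame the whole shortfall from 80% on the figure of 70. That is not right either: at 70 taken at face value, power at 6.43 is already 75.5%.

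The strongest point is the planned baseline adjustment, which could recover precision. With SD × √(1 − r²), a baseline correlation r of about 0.32 would make 6.43 detectable at N = 70. At N = 60 about 0.49 would be needed, since √(1 − (6.43/7.36)²) ≈ 0.49. So it is not shown that the planned adjusted analysis lacks 80% power. This objection stands as a limit on the conclusion. It does not support the stated figure, because the Power paragraph uses an outcome SD of 10 and names no baseline correlation.

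Finally, this is a pilot that the protocol says is not powered for all outcomes. It nevertheless makes a specific 80% claim for the SF-12.

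**Conclusion.** The concern holds in a limited form. The reduction from 80 to 70 is unexplained, and it covers both stated reasons only if both are small: ICC at most 0.14, 0.09, 0.03 or zero at 0%, 5%, 10% or 12.5% loss. Given the protocol's own account of partner similarity, 70 is probably optimistic. It cannot be called an arithmetic error, because neither input is stated.

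Separately, on the stated SD of 10, the claim of 80% power at 6.43 is not met even at 70. Against that corrected baseline, the assumed combinations of 5% to 10% loss with ICC 0.1 to 0.3 that were worked through raise the detectable difference from 6.79 to between 6.84 and 7.67, and lower power at 6.43 from 75.5% to between 75% and 65%. These sizes rest on the assumed loss and ICC and on an unadjusted comparison.

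**What to change.** In the Power paragraph, replace the single figure of 70 with two stated inputs: expected loss, by couple, and the within-couple ICC for the SF-12 outcome. Compute effective N = 80 × (1 − loss)/(1 + ICC). For that N, restate either the detectable SF-12 difference or the power at 6.43, with a small grid covering loss of 0–15% and ICC of 0.05–0.4. If the calculation is to rely on the planned baseline adjustment, state the assumed baseline correlation r and use SD × √(1 − r²).

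The cost is one recalculation and a change of protocol wording. Enrolment stays at 40 couples. The downside is that the stated figure will probably be less favourable, unless a justified baseline correlation offsets it.
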